Proposal for Carolinas Medical Center IRB Approval

Title of the Study: Operative and Non-operative treatment of Traumatic Arthrotomies: A Prospective Observational Study

Date: January 10th, 2019

Version: 4

Abstract

For the last 70 years, orthopaedic dogma has dictated that all injuries that penetrate the joint capsule require formal irrigation and debridement in the operating room to minimize the risk of developing septic complications. The literature supporting this practice is sparse and stems primarily from wartime injuries that may not be generalizable to the smaller, less contaminated arthrotomies seen in the civilian population. Despite the classical teaching of all traumatic arthrotomies requiring irrigation, debridement, and closure in the operating room, numerous surgeons around the country are beginning to treat small traumatic arthrotomies without surgery. The purpose of this study is to evaluate the cost of treatment as well as incidence of adverse events, such as the development of septic arthritis, in patients undergoing operative and non-operative treatment of traumatic arthrotomies.

Background and Rationale

Soft tissue wounds around joints are common injuries that are carefully evaluated to identify intra-articular extension. Wound exploration, imaging, and intra-articular saline load injections are commonly utilized to diagnose the presence of a traumatic arthrotomy. The reason for such diligence is that the treatment is dramatically different for a wound that violates the joint compared to one that does not. As opposed to local wound care for simple soft tissue wounds, traumatic arthrotomies are thought to require formal irrigation and debridement in the operating room to minimize the risk of developing septic arthritis.

Septic Joints

An injury that penetrates the joint capsule and synovium violates the body's natural barriers that protect the joint from external pathogens. Microorganisms from the environment may enter the joint by direct inoculation or by contiguous spread through the now perforated barrier. By bringing patients to the operating room for formal irrigation and debridement, orthopaedic surgeons are theoretically attempting to minimize the burden of contamination and repair the body's natural barriers to reduce the risk of developing an intra-articular infection. Septic arthritis is an orthopaedic emergency that can result in severe cartilage damage causing long-term joint pain, stiffness, and potentially auto-fusion (Chander S, *Curr Infect Dis Rep*, 2011). If not dealt with in a timely manner, intra-articular infections can result in significant long-term disability, and in extreme cases, can result in overwhelming sepsis and death (Chander S, *Curr Infect Dis Rep*, 2011).

Orthopaedic Dogma

Clearly, minimizing the risk of developing septic arthritis is important to every orthopaedic surgeon. Over sixty years ago, Hampton published his observation of a high rate of septic complications in combat injuries that violated the joint (Hampton OP, *JBJS*, 1946). Since then, orthopaedic dogma has dictated that all injuries that violate the joint necessitate formal irrigation and debridement in order to minimize the risk of infectious complications. The literature on the topic is sparse and stems primarily from wartime observations in which the injuries sustained were commonly associated with high levels of contamination, intra-articular fractures, retained foreign bodies, and delayed treatment (Marvel JE, *CORR*, 1977). The characteristics of these injuries may limit the generalizability of these observations to the civilian population, especially for small, mildly contaminated arthrotomies without associated fracture or retained foreign body.

To date, no studies have prospectively evaluated the benefits of operative irrigation and debridement of traumatic arthrotomies compared to non-operative observation with antibiotics. A single study published in 1975 by Patzakis and others showed that patients with open joint injuries treated with operative irrigation and debridement had an infection rate of 2.1%, a value significantly lower than was previously observed in the non-operative cohort of combat injuries (Patzakis MJ, *JBJS*, 1975) (Hampton OP, *JBJS*, 1946) (Marvel JE, *CORR*, 1977). There is little question that large and heavily contaminated arthrotomies benefit from formal irrigation and debridement, but it is unclear if this benefit can be extrapolated to smaller, less contaminated injuries. Nevertheless, orthopaedic surgeons continue to debride and irrigate open joints regardless of the burden of contamination or size of arthrotomy.

Small Arthrotomies are Commonly Missed Injuries

In an effort to identify and treat as many traumatic arthrotomies as possible, orthopaedic surgeons began looking for additional techniques to aid in their diagnosis. After its introduction in 1975, saline arthrograms quickly became the gold standard for the diagnosis of small traumatic arthrotomies (Patzakis and Voit). This doctrine was called into question by Tornetta and others when they showed that saline load arthrograms, as they were commonly performed, had a sensitivity of only 43% (Tornetta P 3rd, *CORR*, 2008). Two years later, Nord and others recommended using 155-ml of saline to diagnose 95% of arthrotomies, a volume more than double what was previously used in clinical practice and not easily tolerated by most patients (Nord RM, *JBJS*, 2009). Most recently, Metzger et. al. demonstrated a false-negative rate of 67% when using 180-mL of saline for their arthrograms, a volume far beyond what would be tolerated in a conscious patient (Metzger P, *JOT*, Epub). Despite missing up to half of all small traumatic arthrotomies for the last 40 years, there has not been an outbreak in patients returning with septic arthritis from missed arthrotomies. The absence of such an occurrence raises the question if it is even necessary to formally debride and irrigate small traumatic arthrotomies in the operating room at a great cost to the patient.

Costs of Arthrotomy

Despite the relative dearth of evidence supporting the practice of formally irrigating and debriding all open joint injuries, significant healthcare expenditures and additional risks of general anesthesia are undertaken to address this problem. Although the administration of general anesthesia has become extremely safe, it still carries the risk of serious consequences such as heart attack, stroke, and even death (Lanier WL, *Am Surg*, 2006)(Botney R, *Int J Radiat Oncol Biol Phys*, 2008). Patients with multiple medical comorbidities are at an even greater risk of a serious perioperative complication (Wolters U, *Br J Anaesth*, 1996).

In addition to the risks of undergoing anesthesia, there are significant costs associated with any operation. A patient diagnosed with an isolated traumatic knee arthrotomy can expect to leave the hospital with a bill of at least \$15,000 based on conservative estimates provided by the Department of Research Finance at Carolinas Medical Center. In an era where healthcare costs are spiraling out of control, determining which interventions are efficacious will be paramount in shaping healthcare resource utilization and maintaining long-term sustainability.

Conclusion

To our knowledge, there is no evidence to support the practice of prophylactic irrigation and debridement of traumatic arthrotomies that would otherwise be amenable to treatment in the emergency department. It is the opinion of the senior authors of this study, who are both experienced orthopaedic traumatologists at high-volume level 1 trauma centers, that small, mildly contaminated traumatic arthrotomies could be treated with antibiotics and close follow-up alone, if they are amenable to closure in the emergency department. Instead of a hospital admission and operative procedure, these patients could be safely discharged from the emergency department with local wound care and antibiotics alone resulting in significant healthcare savings and minimizing the risks of undergoing general anesthesia and a surgical procedure.

Research Plan

Specific Aim 1: To compare the cost of medical care in patients with traumatic arthrotomies treated with surgical irrigation and debridement versus non-operative treatment with local wound care.

Hypothesis 1: Patients with traumatic arthrotomies will have an average hospital bill of \$15,000 less than those treated with surgery.

Specific Aim 2: To determine the incidence of developing a septic arthritis in patients with a non-operatively treated traumatic arthrotomy.

Hypothesis 2: Non-operative treatment of small traumatic arthrotomies will have an extremely low rate (<10%) of subsequent septic arthritis over a 3-month period.

Specific Aim 3: To determine the incidence of developing a septic arthritis in patients with operative treatment of a traumatic arthrotomy.

Hypothesis 3: Operative treatment of traumatic arthrotomies will have an extremely low rate (<5%) of subsequent septic arthritis over a 3-month period.

Specific Aim 4: To determine the need for additional surgery (ex: foreign body removal) in patients with a non-operatively treated traumatic arthrotomy.

Hypothesis 4: Non-operative treatment of small traumatic arthrotomies will have an extremely low rate subsequent surgery over a 6-month period.

Specific Aim 5: To provide a description of traumatic arthrotomies successfully treated non-operatively.

Hypothesis 5: Arthrotomies will be less than 1 cm with a soft tissue injury amenable to closure in the ED. Arthrotomies will be more likely to be due to GSW's and scraping mechanisms rather than direct penetration.

Study Design

Prospective Multi-center Observational Cohort
Retrospective chart review

Study Population

Inclusion Criteria

1. Any patient 18 and older with a traumatic arthrotomy (of any major joint) confirmed by saline load test, direct visualization of a capsular rent or intra-articular contents, or air in the joint on CT or radiographs.
 - a. Major Joints Include:
 - i. Knee
 - ii. Elbow
 - iii. Wrist
 - iv. Shoulder
 - v. Hip
 - vi. Ankle

Exclusion Criteria

1. Patients who will have severe problems with maintaining follow-up

Method for Selecting Samples

Potential patients will be prospectively identified at the time of the initial consultation or at the first clinic follow-up appointment based on the diagnosis of a traumatic arthrotomy (Diagnostic criteria noted in inclusion criteria above).

Patients will be screened by their inclusion and exclusion criteria, and if met will be considered for enrollment in the study.

Retrospective chart review

The study will also conduct a retrospective chart review of patients who presented with a traumatic arthrotomy during the enrollment period, however were unable to be reached for consent after multiple attempts over a period of two years.

Information about injury and treatment outcomes will be collected from the medical record.

Representativeness of the Sample

The study population will be representative of the typical trauma population.

Patients of all ages, genders, ethnicities, and backgrounds will be included in this study. Based on previous clinical series of patients at our institution, we expect that 70% of our patients will be men and 25% minority patients.

Definition of Variables

Outcome Variables

- Primary Outcomes
 - Cost of treatment
 - Adverse Events
 - Development of septic arthritis
 - Return to operating room for any reason (ie: foreign body removal)
 - Rehospitalization
 - Development of osteomyelitis
- Secondary Outcomes
 - Superficial wound infection
 - Extra-articular infection requiring a prolonged course of antibiotics or local wound care.
 - Pain 1 – 10 Scale
 - Current
 - Worst in last 24 hours
 - At rest
 - Bearing weight
 - Ambulating
 - Return to work or previous level of activity

Demographic Variables and Covariates

- Demographic Information

- Age
- Gender
- BMI
- Mechanism of injury
- Smoking Status
- Comorbidities
- Employment status
- Workers compensation status
- Additional Injuries
- Arthrotomy Characteristics
 - Mechanism of arthrotomy
 - Abrasion
 - Laceration
 - Puncture
 - GSW
 - Blast injury
 - Degree of contamination
 - Size of arthrotomy (mm)
 - Shape of arthrotomy
 - Method of Diagnosis
 - Visualization
 - Air on CT or radiograph
 - Saline load
- Treatment Characteristics
 - Antibiotics administered
 - Timing
 - Duration
 - Indication for Surgery
 - OR for additional injury
 - Intra-articular fracture requiring operative fixation
 - Heavily contaminated
 - Intra-articular loose body
 - Large arthrotomy
 - Intra-articular hardware

Potential Confounders

As a prospective observational study, the patient's treatment will not be altered by their inclusion in the study. No guidelines will be provided to influence the treating surgeons' decision making. All surgeons will have treated patients based on their own expert opinion and biases, which will undoubtedly differ between surgeons. The purpose of the study is to show that some traumatic arthrotomies can be treated non-operatively based on surgeon discretion, and having a variety of different arthrotomies will add to the descriptive nature of the study.

The observational nature of this study will introduce a selection bias based on the surgeon's comfort level of treating traumatic arthrotomies non-operatively. Larger and more heavily contaminated arthrotomies will be far more likely to be treated operatively compared to smaller, less contaminated arthrotomies. Any comparisons made between operative and non-operative treatment will have to be made between a matched cohort of arthrotomies of similar severity.

Although the treatment of patients should not be altered by their inclusion in the study, the possibility of a Hawthorne (observer) effect bias exists. The treating surgeon's decision making may potentially be altered by participation in this study.

Patient Safety

Patients involved in the study will not have their medical care altered in any way by their participation. A data safety monitor will be appointed to periodically assess for adverse events. .

Methods

Patient Identification and Enrollment

Patients will be identified at the time of the initial consultation or first clinic follow-up visit based on the presence of a traumatic arthrotomy, of any major joint, based on the criteria outlined above. Patients meeting the inclusion and exclusion criteria will be deemed eligible for the study. Eligible patients will be approached by a member of the treatment team to further discuss the study. If the patient agrees, a member of the research staff will discuss the study in greater detail and obtain informed consent.

Intervention

There will be no alterations in patient care by their inclusion in the study. The attending surgeon will determine the treatment plan, follow-up frequency, and follow-up duration. The need for additional surgery will also be determined by the attending surgeon. The development of septic arthritis or need to proceed to the operating room for foreign body removal will be deemed as adverse events and will be reported to the data safety monitor as they occur.

Data Collection

At the initial consultation, patient demographic information, arthrotomy characteristics, treatment variables, and additional injuries will be obtained. At each follow-up appointments, pain level will be assessed by a member of the treatment team and recorded. Patient will complete the VR-12 to assess quality of health at 3 month after time of their injury. Patients may be followed prospectively for a total of one year after the time of their injury. Patients released from care prior to their one year appointment will be contacted via telephone by a member of the research staff to assess final outcomes. The total cost of care, including hospital and office charges, will be recorded at the one year mark. Patients still requiring care at the 3 month visit as a direct result of treatment of their traumatic arthrotomy will continue to be followed for a total of one year.

Follow-Up

A minimum necessary follow-up of 3 months or 1 year for patient requiring care as a direct result of treatment of their traumatic arthrotomy. Patients released from care after this time period without developing septic arthritis will be considered a successful therapy. If a patient is discharged from clinic prior to 3 months or 1 year, a member of the research team will contact the patient by telephone or by mail to obtain final follow up information.

Data Collection

All data will be entered into REDCap, a web-based data entry and management system that provides logic checks on input and checks for invalid entries. Data will be entered continuously as they are collected and stored in univariate form. We will also run standard checks for outliers, duplicates and other types of errors which may occur within a complex data file. All data files will be password protected and hard copies of blinded patient records will be maintained in locked cabinets in the research office.

Study Duration

Patients will continue to be enrolled for 2-years or until 25 patients are treated non-operatively, whichever comes first.

Statistical Analysis

Standard statistical tests will be used. Descriptive statistics including means and standard deviations, or counts and percentages will be reported. The principal analysis will compare cost of care using logistic regression. Also, demographic and baseline variables will be compared between operative and non-operative patients using t-test and chi-square test where applicable.

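### The anesthetic and surgical harms that the protocol gives as a reason to avoid operating are not among its listed adverse events, so harm from operating is under-counted

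*Combined protocol and SAP*

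**What the plan says.** The Abstract gives the purpose as evaluating cost and the "incidence of adverse events, such as the development of septic arthritis, in patients undergoing operative and non-operative treatment of traumatic arthrotomies". Both groups are covered, and septic arthritis is an example rather than the whole of it.

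Costs of Arthrotomy says of general anesthesia that "it still carries the risk of serious consequences such as heart attack, stroke, and even death", and adds that patients with several comorbidities face a higher risk of a serious perioperative complication. The Conclusion of the background then credits discharge from the emergency department with two benefits: "resulting in significant healthcare savings and minimizing the risks of undergoing general anesthesia and a surgical procedure". Septic Joints says of joint infection that it, "in extreme cases, can result in overwhelming sepsis and death".

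Under Outcome Variables, the primary adverse-event items run from "Development of septic arthritis" through a return to the operating room and rehospitalization to "Development of osteomyelitis". The secondary outcomes are superficial and extra-articular infection, pain, and return to work or activity.

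Patient Safety provides for a data safety monitor who reviews adverse events periodically. Intervention says "The development of septic arthritis or need to proceed to the operating room for foreign body removal will be deemed as adverse events" and that these are reported to the monitor as they happen. Follow-Up describes success as release from care, after the minimum period, without septic arthritis.

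**The concern.** The rationale offers two benefits of not operating. Cost savings became Aim 1 and a primary outcome. Reduced anesthetic and surgical risk has no aim, no outcome and no reporting rule. Comorbidities are recorded as a covariate, but the complication they are said to make more likely is not recorded as an outcome.

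What is at stake is the balance of the harm description. The listed items mainly detect failed infection control and its consequences. If the plan is followed as written, a serious event caused by the index operation or its anesthetic can go untabulated. The operative group then looks safer than it was, which works against the investigators' own argument. Separately, the 3-month septic arthritis rates in Aims 2 and 3 have no stated treatment of patients who die, so two analysts could compute different denominators.

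**Working it through.** The plan states no figure on this point, so there is nothing to reproduce. The check has two parts.

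**1. Named harms against listed items.**

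| Event | Does a listed outcome capture it? | Named for reporting as it happens? |
|---|---|---|
| Non-fatal heart attack or stroke during the index stay | No: not an infection, a return to the operating room or a readmission | No |
| Other serious anesthetic or perioperative event during the index stay | No, unless it leads to a second operation | No |
| The same events after discharge | Only if they lead to readmission | No |
| Death after diagnosed joint infection | Yes, through septic arthritis; the death itself is not listed | The septic arthritis, yes; the death, no |
| Death from another cause | No, unless a listed event came first | No |

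The secondary outcomes change no row. Aim 4 studies additional surgery in the non-operative group only, although the outcome item on returning to the operating room is not restricted by group.

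**2. How many events might be involved.** Study Duration stops enrollment at 2 years or 25 non-operative patients and gives no operative number. No perioperative event rate is given either. Both inputs below are therefore assumptions: n = 50 to 200 operative patients and a rate q of 0.1% or 1%.

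Chance of at least one event = 1 − (1 − q)^n:

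- q = 0.001, n = 50: 1 − 0.999^50 = 4.9%
- q = 0.001, n = 200: 1 − 0.999^200 = 18.1%
- q = 0.01, n = 50: 1 − 0.99^50 = 39.5%
- q = 0.01, n = 200: 1 − 0.99^200 = 86.6%

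The expected count, n × q, runs from 50 × 0.001 = 0.05 to 200 × 0.01 = 2.

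Precision if no event is seen: the one-sided 95% upper bound is 1 − 0.05^(1/n), which is 5.8% for n = 50 and 1.5% for n = 200. Recording these events supports a description of harms. It does not support a comparison of rates.

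**The case against.** The best defense is that the plan is open-ended rather than closed. The Abstract introduces septic arthritis with such-as wording. The Intervention sentence does not say that its two events are the only adverse events, and the monitor's periodic review has no restriction. The listed items apply to both groups, Aim 3 measures septic arthritis after surgery, and reoperation, readmission and infection can themselves be harms of operating. None of the five hypotheses concerns anesthetic risk, and the protocol itself regards modern anesthesia as very safe. Events during the index stay may also reflect other trauma, since surgery for an additional injury and fracture fixation are among the recorded indications.

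Much of this stands, and it rules out several stronger readings that a reader might infer:

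- That none of these events would be counted. Rehospitalization catches those that lead to readmission.
- That the monitor would never learn of a death. The periodic review could bring one to light.
- That a death from joint sepsis leaves no trace. Septic arthritis would normally have been recorded first.
- That a patient who dies before 3 months counts as a treatment success. Such a patient has not been released from care after that period, so the Follow-Up wording is not met.
- That harms are measured in one group only. The gap is in the kinds of harm, not in who is observed.

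The defense does not close the gap. Open wording permits other events to be noticed, but nothing defines them or requires their collection. Rarity and uncertain attribution limit what can be concluded. They are not reasons to leave the events unrecorded.

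**Conclusion.** The point holds in limited form. The protocol intends to evaluate adverse events under both treatments and names heart attack, stroke, death and perioperative complication as risks of operating, yet neither its outcome lists nor its as-they-happen reporting rule names any of them. Non-fatal events during the index stay are the clearest omission. The handling of deaths in the septic arthritis rates is unspecified, which is a different matter from being specified wrongly.

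The direction is an under-count of harm in the operative group. The size cannot be fixed from the documents: on the assumed rates and group sizes, the study might see no such event or one or two. No stated hypothesis test or estimate changes, apart from the septic arthritis denominators once deaths are dealt with. The correction is worth making because it is cheap and the harm description is otherwise incomplete on a matter that the protocol itself raises.

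**What to change.** Under Outcome Variables, add two descriptive safety outcomes for both groups: (a) death from any cause within 3 months of injury; (b) serious anesthetic or perioperative complications, including heart attack and stroke, during the index stay or within 30 days of any arthrotomy-related procedure. Add both to the events that Intervention sends to the data safety monitor. Tabulate them by additional injuries and by indication for surgery, both of which are already collected. Report deaths beside the septic arthritis rate in each group, and do not count them as infection-free. Do not make these new primary comparison endpoints: treatment is not randomized, and index-stay events may be due to other injuries.

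The cost is two more fields taken from hospital records already used for treatment and cost data, with no new visit and no change in care. Three limits should be stated in the report: events will be few, so the result is descriptive; attribution is limited by other trauma; and patients enrolled at their first clinic follow-up have already survived to that visit, so early deaths are under-represented among them.

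### Direct visualization has no setting or timing limit, so an operation can make a patient eligible, and the operative versus non-operative comparison should be restricted to arthrotomies confirmed before the treatment decision

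*Combined protocol and SAP*

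**What the plan says.** The Inclusion Criteria require a traumatic arthrotomy of a major joint "confirmed by saline load test, direct visualization of a capsular rent or intra-articular contents, or air in the joint on CT or radiographs". Any one of the three routes is enough. No setting is named, and nothing requires the finding to precede the treatment decision.

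On timing, Method for Selecting Samples states: "Potential patients will be prospectively identified at the time of the initial consultation or at the first clinic follow-up appointment". A second entry route is retrospective: "The study will also conduct a retrospective chart review of patients who presented with a traumatic arthrotomy during the enrollment period". This covers patients who could not be reached for consent. In both routes, treatment and any operative findings may already be known when eligibility is judged.

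Under Treatment Characteristics, one listed indication for surgery is "OR for additional injury". Under Arthrotomy Characteristics, method of diagnosis has three categories (visualization, air on imaging, saline load). Visualization is not split into bedside and operative.

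On missed wounds, the section on commonly missed injuries says that the saline test as commonly performed "had a sensitivity of only 43" percent. It also reports that one group "recommended using 155-ml of saline to diagnose 95% of arthrotomies", and that another study found a 67% false-negative rate.

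Potential Confounders concedes selection by surgeon comfort, wound size and contamination, and answers it with matching: "Any comparisons made between operative and non-operative treatment will have to be made between a matched cohort of arthrotomies of similar severity".

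**The concern.** In this study surgery is the exposure under comparison. Because visualization is unrestricted, surgery can also be the means by which a patient becomes eligible. Three kinds of wound that look negative at the bedside, or were not fully tested there, then fare differently:

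- **Opened at the initial operation and seen to enter the joint:** eligible, and counted as operative.
- **Treated with local wound care and never opened:** no route to confirmation, so absent from the non-operative group.
- **Treated with local wound care and opened later because of a problem:** can be confirmed then, so entry is conditional on failure. The plan does not say in which group this patient is counted.

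The operative group can therefore hold patients whose non-operative equivalents were never enrolled. The Aim 1 cost contrast, and any matched comparison of adverse events, could then differ for reasons unrelated to how a known arthrotomy was treated. Aims 2 to 5 are each about a single group, so for them the matter is mainly who is represented. The third kind of patient is an exception, because it could add events directly to a single-group rate.

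**Working it through.** The plan gives no figure on this point, so there is none to reproduce. The check asks how large the affected share could be.

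**Inputs**
- s = probability that the non-surgical work-up as a whole (saline load, bedside exploration, imaging) confirms a true arthrotomy. The documents do not give it. They give saline-only values: 43%, 95% at 155 ml, and 33% (100% − 67%). I add 90% as an assumed value for several methods combined.
- p = share of bedside-positive arthrotomies operated on. Assumed 70%.
- q = share of bedside-negative true arthrotomies that are surgically explored, and then seen. Assumed 10%, 20% and 50%.

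**Share of the operative group confirmed only at surgery**

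f = (1 − s)q / [(1 − s)q + ps]

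Example at s = 0.43, q = 0.10: 0.057 / (0.057 + 0.301) = 15.9%.
Example at s = 0.90, q = 0.50: 0.05 / (0.05 + 0.63) = 7.4%.

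| s | q = 10% | q = 20% | q = 50% |
|---|---|---|---|
| 0.33 (saline alone) | 22.5% | 36.7% | 59.2% |
| 0.43 (saline alone) | 15.9% | 27.5% | 48.6% |
| 0.90 (combined, assumed) | 1.6% | 3.1% | 7.4% |
| 0.95 (saline alone, 155 ml) | 0.7% | 1.5% | 3.6% |

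Varying p from 100% to 50% at s = 0.90 moves the q = 10% result from 1.1% to 2.2%, and the q = 50% result from 5.3% to 10.0%. In the group treated without surgery throughout, the corresponding share is zero by construction.

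**Effect on the septic arthritis contrast when treatment has no effect**

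False difference = f × (risk in confirmed wounds − risk in occult wounds).

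With assumed risks of 5% and 1%:
- f = 1.6%: 0.06 percentage points
- f = 7.4%: 0.3 points
- f = 15.9%: 0.6 points
- f = 48.6%: 1.9 points

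If the two risks are equal, the difference is zero whatever f is.

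**Entry conditional on failure**

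Enrollment stops at 2 years or 25 non-operative patients (Study Duration). If one patient confirmed only at a later operation for septic arthritis is counted among 25 non-operative patients, that patient alone contributes 1/25 = 4 percentage points. Hypothesis 2 sets its mark at under 10%. Counted as operative, the same patient raises the operative rate instead. The direction therefore depends on a classification rule that the plan does not state.

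**Can the planned data and analysis deal with it?** The visualization category merges bedside and operative findings. The indication for surgery exists only for operated patients and does not show when the arthrotomy was confirmed. The regression in Statistical Analysis can adjust only for what is recorded.

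**The case against.** The strongest reply is that the protocol never says an arthrotomy found in the operating room is eligible. Direct visualization also covers bedside exploration, which Background and Rationale lists among the usual methods: "Wound exploration, imaging, and intra-articular saline load injections are commonly utilized to diagnose the presence of a traumatic arthrotomy". This stands to the extent that operating-room eligibility is an inference from an open criterion. It is the plain reading all the same, since nothing excludes it and identification may follow surgery.

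A reader might infer that any wound missed by the saline test can never enter the non-operative group. The documents do not support that. Such a wound can still enter through exploration or air on imaging. Only a wound negative or untested on all routes, and never opened later, is shut out.

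A reader might also take 43% as the detection rate and conclude that up to half of the operative group is affected. That figure is for the saline test alone, and the same paragraph also gives 95%. The 67% study, by its title in the citation list, used artificial arthrotomies.

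A third tempting reading is that charges for other injuries measure this bias. Mostly they do not. A patient confirmed on CT who goes to surgery for another injury carries the same extra charges with no problem of eligibility. That is confounding by additional injury.

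Finally, severity matching can pair a small, clean wound found at surgery with a small, clean confirmed wound managed without surgery. If the route of confirmation does not predict outcome after matching, no infection bias remains. That is correct, but the plan gives no basis for assuming it. Small operated wounds are also the natural matches for small non-operative ones, so matching could concentrate the affected patients.

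**Conclusion.** The point holds as a gap in the eligibility rule and in data capture. Eligibility can depend on treatment, and neither the conceded surgeon-comfort bias nor severity matching covers this. The recorded variables would not show which patients are affected.

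The size is uncertain and may be negligible. With combined non-surgical detection near 90% and the assumed surgical shares, the table gives a low single-digit to 7% share of the operative group. Larger shares need detection as poor as the lowest saline-only figures. The direction is not fixed either. It depends on whether occult wounds differ in risk or cost from confirmed ones, and on where patients confirmed at a later operation are counted. The documents therefore do not support a claim that the comparison is materially biased. They support the narrower claim that, as planned, the study could not show whether it is. The remedy is cheap enough to be worth making on that ground.

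**What to change.** Record for every patient whether the arthrotomy was confirmed by findings available before the initial treatment decision (operative or local wound care). Split the visualization category into bedside and operative. For chart-review patients, abstract the same item from the record.

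In Statistical Analysis, state that:
- the Aim 1 cost comparison and any matched operative versus non-operative comparison are restricted to patients confirmed before that decision;
- patients stay in their initial treatment group;
- arthrotomies first confirmed at surgery are reported separately under Aim 3.

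The cost is two REDCap items and a short addition to the analysis text. Care is unchanged and nobody leaves the study. The comparison loses some operative patients, and possibly a few non-operative patients who were confirmed only at a later operation.

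This does not remove extra charges from other injuries in patients confirmed beforehand. For that, use the additional-injuries variable, which is already collected, in the matching or the adjustment.
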